4 STATISTICAL ANALYSES

4.1 GENERAL CONSIDERATIONS

This SAP provides a comprehensive and detailed description of strategy and statistical techniques for the summary and analysis of EFC16461 Study C (omalizumab naïve) only. Study A (omalizumab naïve) and Study B (omalizumab intolerant or incomplete responders) were summarized separately in different SAPs.

In general, continuous data will be summarized using the number of observations available, mean, standard deviation (SD), median, minimum, and maximum. Categorical and ordinal data will be summarized using the count and percentage of participants.

The baseline value of efficacy parameters is defined as the last available value up to randomization date and prior to the first dose of study medication unless otherwise specified. The baseline value of the other parameters is defined as the last available value prior to the first dose of investigational medicinal product (IMP) if the participant is treated, or the last available value up to randomization date if the participant is not exposed to IMP.

Observation period

The observation period will be divided into 4 segments:

- The **pre-treatment period** is defined as the period up to first IMP administration.
- The **treatment-emergent (TE) period** is defined as the period from the first IMP administration to the last IMP administration + 98 days. The treatment-emergent period includes the following 2 periods:
 - The **on-treatment period** is defined as the period from the first IMP administration to the last administration of the IMP + 14 days (+28 days for children <30 kg)
 - The **residual treatment period** is defined as the period from the end of the on-treatment period to the end of the treatment-emergent period.
- The **post-treatment period** is defined as the period from the end of the treatment-emergent period.

The on-study observation period is defined as the time from start of intervention until the end of the study defined as the status date collected on e-CRF page “Completion of End of Study”.

4.2 PARTICIPANT DISPOSITION

The number (%) of participants included in each of the analysis populations listed in [Table 3](#) will be summarized.

Screen failures are defined as participants who consent to participate in the study but are not subsequently randomized. The number (%) of screen failures and reasons for screen failures will be provided in the screened population.

The number (%) of participants in the following categories will be provided:

- Randomized participants
- Randomized but not exposed participants
- Randomized and exposed participants
- Participants who completed the study treatment period as per protocol
- Participants who did not complete the study treatment period as per protocol and main reason for permanent intervention discontinuation including due to COVID-19 pandemic.
- Participants who completed the study period as per protocol
- Participants who did not complete the study period as per protocol and main reason for study discontinuation including due to COVID-19 pandemic.
- Vital status at last study contact

The number of exposed and not randomized participants will also be summarized.

Protocol deviations

Critical and major protocol deviations (automatic or manual) will be summarized in the randomized population and according to COVID-19 impact (ie, deviations related to COVID-19 pandemic and deviations not related to COVID-19 pandemic). In addition, deviations potentially impacting the primary endpoint analysis may be summarized.

4.3 PRIMARY ENDPOINT(S) ANALYSIS

4.3.1 Definition of endpoint(s)

The primary efficacy endpoint is the change from baseline in ISS7 at Week 24.

For EU and EU reference countries, the primary efficacy endpoint is the change from baseline in UAS7 at Week 24.

The once daily UAS is the sum of the daily HSS (ranging from 0 = None to 3 = more than 50 hives) and the daily ISS (ranging from 0 = None to 3 = intense), assessing the 2 key urticaria signs and symptoms which are wheals and itch. The daily UAS scores range from 0 to 6 point/day. The daily UAS scores are summed over 7-day period to create the UAS7, ranging from 0 to 42, and is composed of the HSS7 and ISS7 components.

For daily e-diary endpoints, the baseline values are the sum of the 7 measurements obtained within the 7 days prior to randomization. Note: To be eligible for the study, participants must have no missing e-diary (UAS7 and ISS7) entries in the 7 days prior to randomization.

For the Week 24 score, the sum of the 7 days on and prior to the target visit day will be used (ie, sum of days 163 through 169). If there are less than 7 but at least 4 non-missing scores available, the weekly score is the sum of the available scores in the 7 days, divided by the number of days that have a non-missing score, multiplied by 7. If there are less than 4 non-missing scores, the weekly score is missing. This same rule will be applied for other weekly scores.

4.3.2 Main analytical approach

The primary analysis population for the efficacy endpoints will be the ITT population. The statistical hypotheses for comparing dupilumab against placebo on the primary endpoint of change from baseline in ISS7 at Week 24, and the primary endpoint of change from baseline in UAS7 at Week 24 for EU and EU reference countries are as follows:

- Null hypothesis H0: No treatment difference between dupilumab and placebo
- Alternative hypothesis H1: There is a treatment difference between dupilumab and placebo

For efficacy analysis, [Table 4](#) presents the prohibited and rescue medications where data may be excluded and WOCF values assigned after taking the medication in the main statistical analysis approach due to the impact these medications could have on efficacy. Blinded medical review of participants that receive treatments listed in [Table 4](#) will be implemented before database lock to confirm that the medication was used due to CSU treatment failure and not an unrelated condition. The selected prohibited and/or rescue medications listed in [Table 4](#) are the same as for Study A and Study B SAPs.

Table 4 - Selected prohibited and/or rescue medications impact on efficacy

| Medication | Comment | Intervention in the main statistical analysis (Yes/No) ^a / Selection criteria |
|---|------------------------|--|
| Systemic immunosuppressants (immunosuppressive/immunomodulating drugs) eg, systemic corticosteroids (oral or parenteral [intravenous, intramuscular, SC]), cyclosporine, mycophenolate-mofetil, interferon gamma, Janus kinase inhibitors, azathioprine, methotrexate, hydroxychloroquine, dapsone, sulfasalazine, colchicine, etc. | IMP to be discontinued | Yes (Standardized drug groupings (SDGs) Other immunosuppressants, tumour necrosis factor (TNF) alpha inhibitors, Calcineurin inhibitors, Interleukin inhibitors, Selective immunosuppressants – all Narrow). |
| Antifibrinolytic tranexamic acid and epsilon-aminocaproic acid. | | No |
| Other monoclonal antibodies (which are biological response modifiers). | | Yes (SDG Monoclonal antibodies Narrow). |
| Phototherapy, including tanning beds. | | No |
| IVIG | | Yes (CDG00488 Intravenous immunoglobulin therapy - See Section 5.6). |
| Plasmapheresis | | Yes (CMQ00079 based on the following PTs: Plasmapheresis, Apheresis). |
| Other investigational drugs. | | No, except ones with mechanism of action that may impact efficacy. |
| Topical corticosteroids. | No IMP discontinuation | No |
| Topical calcineurin inhibitors. | | No |
| Topical and oral antihistamines (other than those allowed as background therapy). | | No |
| Routine doses of doxepin (daily or every other day during 5 or more consecutive days). | | No |

| Medication | Comment | Intervention in the main statistical analysis (Yes/No) ^a / Selection criteria |
|---|------------------------|--|
| LTRAs and H2 receptor antagonists, unless stable and taken for diseases other than CSU. | | Yes for LTRAs; No for H2 receptor antagonists (SDG Leukotriene receptor antagonists for obstructive airway diseases Narrow). |
| Additional H1-AH up to 4-fold (2-fold in Japan). Corticosteroids | No IMP discontinuation | No Yes (SDG Corticosteroids Narrow excluding where Route is Topical, Nasal, Respiratory (Inhalation) or Ophthalmic). |
| | | |

^a When yes, if confirmed through blinded medical review the estimand for the intercurrent event handling strategy will be composite. When no, a treatment policy strategy will be applied.

The primary estimand for the primary endpoint is the treatment policy/composite approach.

The primary efficacy endpoints will be analyzed using an analysis of covariance (ANCOVA) model with the baseline value of the primary endpoint, intervention group, presence of angioedema at baseline, and region as covariates, with intercurrent events and missing data being handled by a hybrid method of the worst-observation carried forward (WOCF) and multiple imputation. For participants taking selected prohibited medications and/or rescue medications (see [Table 4](#)), their data after the medication start date will be excluded, and the worst postbaseline value on or before the time of the medication usage will be assigned to the Week 24 value (for participants whose postbaseline values are all missing, the baseline will be used). Participants who discontinue the intervention prematurely are encouraged to follow the planned clinical visits and in these participants who did not take the selected prohibited medications and/or rescue medications, all data collected after intervention discontinuation will be used in the analysis. For these participants, missing data may still happen despite all efforts to collect the data after intervention discontinuation. For participants who discontinue study intervention due to lack of efficacy, all data collected after discontinuation will be used in the analysis, and a WOCF approach will be used to impute missing Week 24 value if needed (ie due to study discontinuation). For participants who discontinued study intervention for reasons other than lack of efficacy, a multiple imputation approach will be used to impute the missing Week 24 value. This multiple imputation will include all participants except participants who have taken the selected prohibited medications and/or rescue medications on or before Week 24 and will also exclude participants who discontinued study intervention due to lack of efficacy on or before Week 24.

Each of the imputed complete data will be analyzed by fitting an ANCOVA model as described above. Statistical inference obtained from all imputed data will be combined using Rubin's rule. Descriptive statistics including number of participants, mean, standard error, and least squares (LS) mean changes (and standard error) score will be provided. In addition, difference of the dupilumab group against placebo in LS means and the corresponding 95% confidence intervals (CI) will be provided along with the p-values.

See [Section 5.5](#) for the sample SAS code for the imputation and how the analysis model will be built.

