### Methods of assigning patients to treatment group

The randomized intervention kit number list is generated centrally by Sanofi and IMPs (dupilumab 300 mg, dupilumab 200 mg, or their matching placebo) are packaged in accordance with this list. The randomization and intervention allocation are performed centrally by an IRT. The IRT generates the participant randomization list and allocates the intervention number and the corresponding intervention kits to the participants according to it.

Participants will be randomized in a 1:1 ratio treatment arm described in [Table 3](#).

The randomization will be stratified first by age (adults versus adolescents versus children in Study A and Study C and adults versus adolescents in Study B; up to approximately 5% of total sample size for children and approximately 5% of total sample size for adolescents in Study A and Study C; up to approximately 5% of total sample size for adolescents in Study B). In adults, randomization will be stratified further by country (Study A, B and C) and presence of angioedema at baseline (Study C only). In adolescents/children  $\geq 6$  to  $< 12$  years of age, randomization will not be stratified further. In Study A, overall 52% of participants received H1-AH at recommended doses as background therapy, and 45% of participants presented with angioedema at baseline. To maintain consistency between the study population in studies A and C, and reflect the real-life distribution of patients with angioedema and uncontrolled by both standard dose or maximal H1-AH therapy, it is planned that Study C would include not more than

approximately 50% (n=75) of participants having their H1-AH therapy at recommended doses (for more details please see Section 6.1.2), and not less than approximately 30% (n=45) but not more than approximately 45% (n=68) of participants presenting with angioedema at baseline.

It is anticipated that approximately 30%-40% of enrolled participants will have angioedema.

A randomized participant is defined as a participant who has been allocated to a randomized intervention regardless whether the treatment was administered or not (ie, participant registered by the IRT). A participant cannot be randomized more than once in the study.

Investigational medicinal products will be dispensed at the study visits summarized in the Schedule of activities (SoA).

Returned IMP should not be re-dispensed to the participants.

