	
participants, missing data may still happen despite all efforts have been tried to collect the data after treatment discontinuation. For participants who discontinue due to lack of efficacy, all data collected after discontinuation will be used in the analysis, and a WOCF approach will be used to impute missing Week 24 value if needed. For participants who discontinue not due to lack of efficacy, a multiple imputation approach will be used to impute missing Week 24 value, and this multiple imputation will use all participants excluding participants who have taken the selected prohibited medications and/or rescue medications on or before Week 24 and excluding participants who discontinue due to lack of efficacy on or before Week 24. Each of the imputed complete data will be analyzed by fitting an analysis of covariance model with the baseline value of the primary endpoint, treatment group, presence of angioedema at baseline, and region (combined countries) as covariates. Statistical inference obtained from all imputed data will be combined using Rubin's rule. Descriptive statistics including number of subjects, mean, standard error, and least squares (LS) mean changes (and standard error) score will be provided. In addition, difference of the dupilumab group against placebo in LS means and the corresponding 95% confidence intervals (CI) will be provided along with the p-values.
 
Sensitivity analysis
 
Tipping point analyses and other sensitivity analyses will be performed to confirm robustness of the results with respect to the missing data handling. Details of the sensitivity analyses will be provided in the SAP.
 
Subgroup analysis
 
To assess the consistency in treatment effects across different subgroup levels, subgroup analyses will be performed for the primary efficacy endpoint with respect to age group, gender, region, and other factors that will be specified in the SAP.

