1 INTRODUCTION

1.1 STUDY DESIGN

This is a master protocol composed of 3 studies of similar design, 2 studies in participants who are omalizumab naïve (Study A and Study C) and 1 study in participants who are omalizumab intolerant or incomplete responders (Study B). Study A and Study C will include adults, adolescents (≥ 12 to < 18 years) and children (≥ 6 to < 12 years). Study B will include adults and adolescents. The three studies are 24-week, double-blind, randomized, placebo-controlled studies to evaluate the use of dupilumab in participants with chronic spontaneous urticaria (CSU) who remain symptomatic despite the use of H1-antihistamines (H1-AH).

After a screening period of 2 to 4 weeks, participants are centrally randomized (using permuted block randomization schedule) via interactive response technology (IRT) in a 1:1 randomization ratio to dupilumab (300 mg q2w for adults and adolescents ≥ 60 kg after a loading dose of 600 mg on Day 1; 200 mg q2w for adolescents < 60 kg and children ≥ 30 kg after a loading dose of 400 mg on Day 1; or 300 mg q4w for children < 30 kg and ≥ 15 kg after a loading dose of 600 mg on Day 1) or placebo over a 24-week treatment period. Randomization is stratified first by age (adults versus adolescents versus children in Study A and Study C, adults versus adolescents in Study B; up to approximately 5% of total sample size for children and approximately 5% of total sample size for adolescents). In adults, randomization is stratified further by country (Studies A, B, and C) and presence of angioedema at baseline (Study C only). In adolescents/children ≥ 6 to < 12 years of age, randomization is not stratified further.

The total anticipated number of participants across the 3 studies is approximately 384 randomized participants (130 participants in Study A, 104 participants in Study B and 150 participants in Study C).

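### Study C's primary ANCOVA leaves out age group, the first randomisation stratum: no threat to validity, a small and uncertain gain in precision, and a one-term fix

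*SAP*

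**What the plan says.** **Randomisation.** Study C SAP Section 1.1: "Randomization is stratified first by age (adults versus adolescents versus children in Study A and Study C". The next level applies to adults only: "In adults, randomization is stratified further by country (Studies A, B, and C) and presence of angioedema at baseline (Study C only". Protocol Section 6.3 agrees: "The randomization will be stratified first by age". The planned size of the younger strata is "up to approximately 5% of total sample size for children and approximately 5% of total sample size for adolescents".

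**Primary model.** Study C SAP Section 4.3.2 specifies an ANCOVA with the baseline score, treatment group, "presence of angioedema at baseline, and region as covariates". Protocol Table 7 has the same list: "baseline value of the primary endpoint, treatment group, presence of angioedema at baseline, and region (combined countries) as covariates".

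**Imputation.** Study C SAP Section 5.5, step 2, describes the regression as adjusting for treatment group, region, angioedema and the baseline value. The code itself is redacted. Step 2 of the tipping-point analysis in Section 4.3.3 also has no age term.

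**Age elsewhere.** The subgroup cuts in Section 4.3.5 are the median and 65 years. Sections 4.3.5 and 4.4.2 add separate analyses of the primary endpoint and the hierarchical secondary endpoints in adults and adolescents. None of these sections explains why age group is left out of the main model.

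**The concern.** A stratified randomisation forces balance between arms within each stratum. If the stratum predicts outcome and the model omits it, the between-stratum variation stays in the residual error although the design has removed it from the treatment comparison. The reported standard error then overstates the real uncertainty.

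The plan represents its other strata. Angioedema, a stratum that Amendment 5 introduced for Study C, is in the model. Country is there as region. Age, the top-level factor, is not. Some difference by age is conceivable: non-adult dosing varies with weight, and caregivers may help younger participants to read and understand the questionnaires (Protocol Section 8). At stake is a little precision on the primary test and agreement between analysis and design.

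**Working it through.** **Inputs**
- Treatment difference 4.23 and SD 7.5 on ISS7, two-sided alpha 0.05, 10% dropout, 75 per group, 90% power: Protocol Section 9.2. The matching Study C SAP section is partly redacted.
- Non-adult share p: 6/138 = 0.043 in Study A (4 adolescents and 2 children, Protocol Section 2.1); about 0.10 at the planned maximum, or 15 of 150.
- Adult versus non-adult difference in Week 24 change, δ: not in the documents. Assumed 0 to 5 ISS7 points.

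**1. The plan's own figure.** Effect size 4.23/7.5 = 0.564. Normal approximation: n = 2(1.960 + 1.282)²/0.564² ≈ 66.1, so 67 per group; 67/0.9 = 74.4, so 75. With 75 × 0.9 = 67.5 evaluable per group, the t-test has 90.2% power. The figure reproduces.

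**2. Effect of adding a two-level age factor.** The share of outcome variance explained is R² = p(1 − p)δ²/7.5², and the standard error is multiplied by √(1 − R²). Without age it is 7.5 × √(2/67.5) = 1.291. Power is by noncentral t with one degree of freedom removed.

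| p | δ (points) | R² | SE | SE reduction | Power |
|---|---|---|---|---|---|
| either | 0 | 0 | 1.291 | 0% | 90.2% |
| 0.043 | 2 | 0.003 | 1.289 | 0.15% | 90.3% |
| 0.043 | 5 | 0.018 | 1.279 | 0.9% | 90.7% |
| 0.10 | 2 | 0.006 | 1.287 | 0.3% | 90.4% |
| 0.10 | 5 | 0.040 | 1.265 | 2.0% | 91.3% |

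The gain is 0 to 0.5 power points at Study A's mix and 0 to 1.1 at the planned maximum. These are upper limits, because R² here is marginal and baseline score and region may already absorb part of any age effect.

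**3. Validity, by simulation.** Assumptions: 135 evaluable participants, 7 adolescents and 7 children; nine countries in four regions; adults stratified by country and angioedema; permuted blocks of 4 (block size assumed); 6,000 runs per scenario. Age entered as three levels.

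| Non-adult shift | Type I error, without / with age | Power, without / with age |
|---|---|---|
| 0 | 4.8% / 4.9% | 89.9% / 90.0% |
| 0.5 SD | 4.6% / 4.9% | 89.6% / 90.0% |
| 1 SD | 3.9% / 4.9% | 88.1% / 90.0% |

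The Monte Carlo error on a 5% rate is √(0.05 × 0.95/6000) ≈ 0.3 points. The treatment estimate was unbiased in every case. At a 0.5 SD shift without age, the mean model SE was 0.175 against a true sampling SD of 0.173 (in units of the residual SD): too large, but only just.

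**4. Side effect on per-arm LS means.** If LS means weight the two age levels equally, the variance of an arm's LS mean is 7.5² × [1/75 + (0.5 − p)²/(150p(1 − p))], taking treatment and age only and 75 per arm. Without age the SE is 7.5/√75 = 0.87. With 15 minors (p = 0.10) it is √(56.25 × 0.02519) = 1.19; with 6 (p = 0.04) it is √(56.25 × 0.05007) = 1.68. The SE of the treatment difference stays at 7.5 × √(2/75) = 1.22.

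**The case against.** **No age effect is documented.** Protocol Section 2.3 reports similar efficacy in adults, adolescents and children in atopic dermatitis and asthma, and Section 4.3 expects the doses to saturate the receptor in most patients. The assumed upper limit of 5 points exceeds the whole planned treatment effect of 4.23. This stands, and it is why the gain is given as a range from zero. It does not exclude a prognostic age effect in urticaria.

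**The strata are tiny.** At least about 90% of participants sit in one age stratum, and Study A had only 6 minors. Leaving out such a sparse factor is a defensible judgement. But the pooled term costs one degree of freedom, and power is unchanged when age carries no information.

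**Adding age could harm the reported arm means.** The Study A and B sample code requests LS means without observed margins. If Study C does the same, each arm's mean becomes a 50:50 average of adults and minors, with the larger SEs shown above. This is correct, and observed-margin weights resolve it.

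**The covariates are fixed in the protocol and shared with Study A.** True. The change is a small departure that has to be recorded.

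**Age is examined elsewhere.** The adult and adolescent analyses restrict the population; they do not adjust the primary test.

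A reader might infer that a mismatch between model and randomisation invalidates the primary test. The documents and the simulation do not support that: the error runs only in the conservative direction.

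**Conclusion.** The mismatch is real and minor. Age group is the first randomisation factor and the only one not represented in the primary model or the imputation regression. The consequence is at most a slightly conservative test. The sample size of 75 per group and the alpha level are unaffected.

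The size rests on an assumed age difference that the documents do not supply. Over 0 to 5 ISS7 points, the standard error falls by 0 to 1% at 4.3% non-adults and by 0 to 2% at about 10%, so the most to be gained is about one power point. A reader might also infer that the plan gives away worthwhile precision at no cost. That goes too far: the gain could be nil, and the term has a small price in degrees of freedom and in how the arm means are reported. What remains is a low-cost improvement that brings the analysis into line with the design.

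**What to change.** Before unblinding, amend the Study C SAP as follows:

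- Add age group (adult versus under 18, pooled because the adolescent and child strata are sparse) as a fixed effect in the primary ANCOVA (Section 4.3.2), in the continuous endpoints of the hierarchy (Section 4.6), and in the imputation regression (Section 5.5). Keep the tipping-point imputation step in Section 4.3.3 in line with it.
- Specify observed-margin weights for the per-arm LS means.
- Leave the CMH strata as they are, to avoid thinning them further.
- Record the departure from the protocol's and Study A's covariate list in Section 5.2, since the SAP's version history states no major changes from the protocol.

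**Cost:** one model term, one degree of freedom and a short entry in the SAP. There is no gain if age carries no information or if very few minors enrol.
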